11.1.2. Male Subjects

To prevent pregnancy in a female partner or to prevent exposure of any partner to the study treatment from a male subject’s semen, male subjects must use one of the following contraceptive methods:

- Abstinence, defined as sexual inactivity consistent with the preferred and usual lifestyle of the subject. Periodic abstinence (e.g., calendar, ovulation, symptothermal, post-ovulation methods) and withdrawal are not acceptable methods of contraception.

Complete abstinence from sexual intercourse for 14 days prior to first dose of study treatment, through the dosing period, and for at least 45 days or 5 half-lives (whichever is longer) after the last dose of study treatment.

- Condom (*during non-vaginal intercourse with any partner - male or female*) **OR**
- Double-barrier method: condom and occlusive cap (diaphragm or cervical/vault caps) plus spermicidal agent (foam/gel/film/cream/suppository) (*during sexual intercourse with a female*).

11.2. Lactation Restrictions

Female subjects who are lactating must discontinue nursing prior to the first dose of study treatment and must refrain from nursing throughout the treatment period and for at least 45 days or 5 half-lives (whichever is longer) following the last dose of study treatment.

12. DATA MANAGEMENT

For this study, data will be collected using defined eCRFs, transmitted electronically to GSK and combined with data provided from other sources in a validated data system.

Management of clinical data will be performed in accordance with applicable GSK standards and data cleaning procedures to ensure the integrity of the data, e.g. removing errors and inconsistencies in the data. AEs and concomitant medications terms will be

coded using Medical Dictionary for Regulatory Activities (MedDRA) and an internal validated medication dictionary, GSK Drug. eCRFs, including queries and audit trails, will be retained by GSK, and copies will be sent to the investigator to maintain as the investigator copy.

When laboratory samples (i.e., hematology and clinical chemistry) are analyzed by a central laboratory the results will be stored in a database maintained by the central laboratory and transferred to GSK at agreed times. When laboratory samples are analyzed by a local laboratory, the laboratory normal ranges will be provided to GSK and the results will be entered into the eCRF.

In all cases, subject initials will not be collected or transmitted to GSK according to GSK policy.

13. DATA ANALYSIS AND STATISTICAL CONSIDERATIONS

13.1. Hypothesis(es)

13.1.1. Part 1: Dose-Escalation Phase

With respect to primary objectives and endpoints, no specific hypotheses are being tested during the dose escalation portion of this study. The primary focus will be on determining the safety profile of GSK2849330 and recommended dose for further exploration. Most of the analyses will be descriptive or exploratory.

13.1.2. Part 2: Molecularly-Defined Tumor Histology Groups

For the groups in Part 2, hypothesized clinical benefit rates are provided in Section [13.2.2](#). A test that the clinical benefit rate is less than or equal to the null hypothesis rate versus the clinical benefit rate is greater than or equal to the alternative rate is being performed using the stopping rules provided. Descriptive statistics will be used to describe the observed response rates at the dose used in each of the groups.

13.2. Sample Size Determination

13.2.1. Part 1: Dose-Escalation Phase

The total number of subjects in the Part 1 dose escalation will depend on the number of dose escalations needed, but the minimum number of subjects anticipated to complete dose escalation is 13 and the anticipated number of subjects is approximately 34 subjects. The selection of sample size 34 is based on the goal of fully exploring available dose ranges for purposes of selecting an appropriate regimen(s) for Part 2. This will include a number of cohorts to establish an initial understanding of the dose-response relationship as well as to evaluate a range of PD biomarkers that may reveal the biological activity of GSK2849330. The initial cohort (1.4 mg/kg) will have 1 subject and Cohorts 2 through 5 will have 3 subjects in the dose escalation phase and up to an additional 3 subjects with

evaluable pre- and on-treatment paired biopsies in each of these cohorts for the PK/PD cohorts. See Section 3.3 and Table 3 for additional details. The actual number of cohorts and subjects will depend in part on the observed toxicity and the PK and PD observed during the dose escalation.

Simulations were conducted to determine the average sample size and percentage of time each dose was selected under 3 different scenarios: almost no toxicity scenario, little toxicity scenario and moderate toxicity scenario. For each scenario, 5000 clinical trials were simulated using the planned doses. Details are provided in Table 14.

The specified prior probabilities discussed in Section 3.3 were used to determine an explicit equation for the prior distribution using the FACTS software. The parameters (s.d.) of the explicit distribution are $\alpha=-5.334(1.9913)$, $\ln(\beta)=-0.0579(0.1018)$, and $\rho=-0.9977$ where α and $\ln(\beta)$ are distributed as bivariate normal with correlation ρ .

Table 14 Simulation Results for Various Scenarios

Dose (mg/kg)	Scenario 1: Almost No Toxicity		Scenario 2: Little Toxicity		Scenario 3: Moderate Toxicity	
	True DLT Rate	Percent of Trials Selecting Dose as MTD (%)	True DLT Rate	Percent of Trials Selecting Dose as MTD (%)	True DLT Rate	Percent of Trials Selecting Dose as MTD (%)
1.4	0.00005	0	0.0005	0.8	0.05	5.2
3	0.0005	0	0.1	10	0.1	14.2
10	0.005	0.2	0.2	33	0.2	37.4
30	0.055	99.8	0.25	56.2	0.3	43.2

The average sample size over the 5000 clinical trials simulated under Scenarios 1-3 was 15.2, 15.5, and 15.1 respectively.

13.2.2. Part 2: Molecularly-Defined Tumor Histology Groups

Once the recommended dose(s) and schedule(s) is/are confirmed from Part 1, at least 12 and up to 30 subjects per group will be enrolled at that dose(s) in Part 2, guided by decision rules defined in Section 13.6.2. These guidelines are based on the predictive probabilities of success if enrollment were to continue to 30 subjects using the methodology of [Lee, 2008].

The null hypothesis is:

$$H_0: p \leq 10\%$$

The alternative hypothesis is:

$$H_A: p \geq 30\%$$

Starting with a group of 12 subjects and allowing for a maximum sample size of 30, this design will have a type I error rate (α) of 0.15 and 94% power. Group enrollment will be stopped early for futility if the predictive probability of success is less than 6%. The trial would not stop early for success. The Bayesian Prior was Beta (0.2, 0.8), a weak prior with a mean response rate of 20%. The group outcome will be considered successful if the posterior probability of ($P > 0.10 \mid \text{observed data}$) is $\geq 80\%$. The futility boundary described in Section 13.6.2 was calculated based on the optimizing criterion of maximizing the power under the alternative hypothesis.

Under the null hypothesis, the expected sample size is 20 subjects and the probability of early termination is 77%. Under the alternative hypothesis, the expected sample size is 29 subjects and the probability of early termination is 5%.

13.3. Sample Size Sensitivity

No analysis of sample size sensitivity was performed.

13.3.1. Sample Size Re-estimation

Sample size re-estimation is not planned for this study.

13.4. Data Analysis Considerations

Data will be listed and summarized according to GSK integrated data standards library (IDSL) reporting standards where applicable. Complete details will be provided in the RAP.

13.4.1. Analysis Populations

The **All Treated Population** is defined as all subjects who receive at least one dose of GSK2849330. Safety will be evaluated based on this analysis population.

The **Efficacy Population** will consist of all subjects from the All Treated Population for whom at least one post-dose tumor assessment by CT scan has been performed.

The **PK Population** will consist of all subjects from the All Treated Population for whom at least one post-dose PK sample is obtained and analyzed.

Additional analysis populations may be defined in the RAP.

13.4.2. Analysis Data Sets

The construction of datasets relating to the reporting and analysis of study data will be performed in accordance with all applicable GSK standards and procedures.

13.4.3. Withdrawal

Reason for subject withdrawal will be listed.

13.4.4. Missing Data

Missing data will not be imputed. Where appropriated, available data will be summarized over specified intervals (*e.g.*, from start of treatment until withdrawal from study) using suitable summary statistics.

13.4.5. Derived and Transformed Data

The PK parameters, AUC, C_{max}, and MRT will be log-transformed prior to analysis.

13.4.6. Assessment Windows

Safety assessments that occur prior to the administration of study drug will be considered screening assessments. Safety assessments that occur after dosing has begun will be considered as having occurred while on treatment.

Disease assessments will be distinguished as belonging to either screening, continued therapy or post-study phases of the study.

13.4.7. Other Issues

Data from participating centers will be pooled prior to analysis. It is anticipated that subject accrual may be limited across centers and summaries of data by center would likely not be informative. Therefore, these summaries will not be provided.

Demographic and baseline characteristics will be summarized.

For PK analyses, assay values below the quantitative limit (BQL) will be handled as described in the GSK CPK/M&S PK methods.

13.5. Treatment Comparisons

13.5.1. Primary Comparisons of Interest

Several dose levels and regimens of GSK2849330 are being investigated. No formal comparisons will be performed regarding differences between the dose levels. Safety, PK, PD biomarker, and clinical benefit summaries will be provided by dose level of GSK2849330.

13.5.2. Other Comparisons of Interest

In Part 1, PK parameters including, but not limited to, AUC(0-t), AUC(0-τ), AUC(0-∞), C_{max}, t_{max}, and MRT of GSK2849330 will be descriptively compared between dose

levels in tabular or graphic formats. In Part 2, other safety, PK and clinical activity data than the primary endpoints will also be evaluated and compared between different treatment groups.

- PK: PK parameters including, but not limited to, AUC(0-t), AUC(0- τ), AUC(0- ∞), Cmax, tmax, and MRT of GSK2849330 will be descriptively compared between dose levels in tabular or graphic formats.
- PD biomarker: Changes from baseline in PD markers, the markers of inflammatory response activation from blood and markers in skin and tumor biopsies will be evaluated and summarized for each dose cohort or group.
- Clinical anti-cancer activity: The number of CRs, PRs, stable diseases (SDs) and PDs for each dose cohort or group will be listed using RECIST, irRC, and mRECIST and summarized if appropriate.

13.6. Interim Analysis

Ongoing examination of safety, PK and PD data will occur while the study is being conducted. In Part 1, PK parameters will also be evaluated and compared among different treatment cohorts.

13.6.1. Part 1: Dose-Escalation

In Part 1 (Dose-Escalation), an interim analysis will be performed to determine if a dose-escalation is appropriate and to be informed of the data reviewed to support the dose-escalation decision following the completion of each dose cohort. The primary driver for the dose-escalation decision(s) in Part 1 will be safety and tolerability of each dose cohort. Further details regarding such analyses will be provided in the RAP.

13.6.2. Part 2: Molecularly Defined Tumor Histology Groups

For each of the groups in Part 2, response data will be reviewed on an ongoing basis. After the initial 12 subjects have been enrolled at the recommended dose, the number of responses observed will be compared with the stopping rules provided in [Table 15](#) and [Figure 1](#) below.

Table 15 xStopping rules for each expansion group

Number of Subjects Enrolled	Stop for Futility if \leq this number of responders is observed
12	0
16	1
22	2
27	3
30	4

Figure 1 Diagram of Stopping Rules for each Group

Number of Subjects	Number of Responders					
	0	1	2	3	4	5
12	Red					
13	Red					
14	Red					
15	Red					
16	Red	Red				
17	Red	Red				
18	Red	Red				
19	Red	Red				
20	Red	Red				
21	Red	Red				
22	Red	Red	Red			
23	Red	Red	Red			
24	Red	Red	Red			
25	Red	Red	Red			
26	Red	Red	Red			
27	Red	Red	Red	Red		
28	Red	Red	Red	Red		
29	Red	Red	Red	Red		
30	Red	Red	Red	Red	Red	

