
STATISTICAL METHODS
	
The total number of subjects in the Part 1 dose escalation will depend on the number of dose escalations needed, but the minimum number of subjects anticipated to complete dose escalation is 13. A target maximum of 21 additional subjects with evaluable pre- and on-treatment tumor biopsies may be enrolled in the PK/PD cohorts. Cohort size is based on feasibility and the objective to provide an initial characterization of safety and PK/PD information that will inform dose regimen selection for Part 2.
 
In Part 2, at least 12 and up to 30 subjects will be enrolled in each group. Each group will include a futility analysis, whereby no additional subjects will be enrolled in a group if futility criteria are met, as defined in Section 13.6.2.
 
The null hypothesis is:
 
$H_0: p \leq 10\%$
 
The alternative hypothesis is:
 
$H_A: p \geq 30\%$
 
Starting with a group of 12 subjects and allowing for a maximum sample size of 30, this design will have a type I error rate (α) of 0.15 and 94% power. Group enrollment will be stopped early for futility if the predictive probability of success is less than 6%. The Bayesian Prior was Beta (0.2, 0.8), a weak prior with a mean response rate of 20%. The group outcome will be declared successful if the posterior probability of

($P > 0.10$ | observed data) is $\geq 80\%$.

Under the null hypothesis, the expected sample size is 20 subjects and the probability of early termination is 77%. Under the alternative hypothesis, the expected sample size is 29 subjects and the probability of early termination is 5%.

The **All Treated Population** is defined as all subjects who receive at least one dose of GSK2849330. Safety will be evaluated based on this analysis population.

The **Efficacy Population** will consist of all subjects from the All Treated Population for whom at least one post-dose tumor assessment by CT scan has been performed.

The **PK Population** will consist of all subjects from the All Treated Population for whom at least one post-dose PK sample is obtained and analyzed.

Additional details of the statistical analysis plan will be provided in the reporting and analysis plan (RAP).

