3.4. Part 2: Molecularly-Defined Tumor Histology Groups

Part 2 can begin once the recommended dose and schedule is identified in Part 1. It is possible that more than one dose and/or schedule will be evaluated in Part 2 if available PK, PD and safety data suggest that multiple doses and schedules have desirable biologic activity or if an MTD cannot be established.

The selected dose level(s) will be evaluated in Part 2 for confirmation of safety and tolerability, as well as preliminary assessment of clinical benefit, in at least 4 molecularly-defined tumor histology groups of subjects with HER3 or HER3 and NRG1 expressing tumors. Group 1 will include subjects with HER3- expressing melanoma. Group 2 will include subjects with HER3-expressing gastric cancer. Group 3 will include subjects with HER3 expressing and NRG1-expressing cancers of the head and neck. Group 4 will include subjects with HER3 expressing and NRG1-expressing NSCLC. All subjects must have archival tissue available for HER3 and if required NRG1 testing or be willing to undergo a tumor biopsy using a procedure that is safe for the subject, to provide a sample for testing.

Each group will initially enroll 12 subjects with the option of expanding to a maximum of 30 subjects if futility criteria are not met using well established methodology of [Lee, 2008] (See Section 13.2.2 and Section 13.6.2 for additional details).

Subjects will be required to have disease amenable to biopsy and agree to pre-and on-treatment tumor biopsies, using a procedure that is safe for the subject. Pre-and on-treatment biopsies are mandatory for all subjects in all groups. GSK will closely monitor and evaluate the collection of evaluable biopsies and will notify the participating centers of any change to the collection requirements for any or all groups.

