5. STUDY POPULATION

5.1. Number of Subjects

The number of dose levels and the level at which the MTD is reached cannot be determined in advance. An adequate number of subjects will be enrolled into the study to establish the recommended dose(s) for further study. It is estimated that approximately 13 subjects will be enrolled in Part 1 dose escalation if there are no DLTs observed; if there are any DLTs observed, more than 13 subjects can be enrolled in dose escalation. Up to an additional 21 subjects with evaluable pre- and on-treatment paired biopsies can be enrolled for the purpose of the PK/PD cohorts in Part 1. Therefore, up to approximately 34 subjects may be enrolled into Part 1 (dose-escalation and PK/PD cohorts) of the study; however, additional dose escalation cohorts may be enrolled to allow for further evaluation of additional dose levels/regimens if warranted.

In Part 2 of the study, there will be at least 4 molecularly-defined tumor histology groups. It is estimated that a minimum of 12 subjects will be enrolled in each group with a maximum of approximately 30 subjects if futility criteria are not met. Therefore, approximately 120 subjects may be enrolled in Part 2 and approximately 154 subjects may be enrolled in the entire study; however, this number will be considerably fewer if futility conditions are met for any group in Part 2 (see Section 3.4, Section 13.2.2, and Section 13.6.2). Additional groups of tumor histologies predicted to be sensitive to the study drug based on emerging nonclinical or clinical data may be added to Part 2.

In Part 1 (dose escalation) of the study, if subjects prematurely discontinue for reasons other than toxicity, additional subjects may be enrolled as replacement subjects and assigned to the same treatment cohort at the discretion of the Sponsor in consultation with the investigator. Subjects may also be replaced in Part 2 of the study for the purpose of testing futility or to facilitate collection of sufficient tumor biopsies for exploratory analyses.

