7.8. Evaluation of Anti-Cancer Activity

Disease assessment may include imaging (e.g., CT scan, MRI, bone scan, plain radiography) and physical examination (as indicated for palpable/superficial lesions). Disease assessment will be completed within 4 weeks prior to the first dose of GSK2849330, then every 8 or 9 weeks thereafter, and at the final study visit. See the Time and Events Tables (Section 7.1) for the schedule of assessments of anti-cancer activity. Assessments must be performed on a calendar schedule and should not be affected by dose interruptions/delays. For post-baseline assessments, a window of ± 7 days is permitted to allow for flexible scheduling. If the last radiographic assessment was more than 8 weeks prior to the subject's withdrawal from study, progressive disease (PD) has not been documented, and the subject has not started subsequent anti-cancer therapy, a disease assessment should be obtained at the Follow-up visit or the Post-study visit.

In addition to the above, a MRI with contrast should be considered to rule out the presence of brain metastases. CT scans with and without contrast may be performed if a MRI is contraindicated or otherwise unavailable.

For purposes of determining futility, disease progression and response evaluations will be determined according to the definitions established in the Response Evaluation Criteria in Solid Tumors (RECIST 1.1) [Eisenhauer, 2009] (see Appendix 5). Exploratory assessment of response according to immune-related response criteria (Appendix 6) and mRECIST (Appendix 7) [Lencioni, 2010] should also be recorded. Subjects whose disease responds (either CR or PR) should have a confirmatory disease assessment performed at least 4 weeks after the date of assessment during which the response was demonstrated. More frequent disease assessments may be performed at the discretion of the investigator. To ensure comparability between the baseline and subsequent assessments, the same method of assessment, the same technique and the same radiologist should be used when assessing response. Images should be retained until study completion to facilitate central review if requested. Tumor markers should be followed serially per institutional guidelines and recorded in the eCRF where part of standard practice.

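### The Part 2 futility boundaries are indexed on subjects enrolled, not assessed, so read literally they stop an active group more often than the stated 5%

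*Protocol*

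**What the plan says.** Protocol 13.6.2 triggers the first futility comparison as follows: "After the initial 12 subjects have been enrolled at the recommended dose, the number of responses observed will be compared with the stopping rules". The left-hand column of Table 15 is headed "Number of Subjects Enrolled"; the axis of Figure 1 mentions subjects without saying enrolled or assessed. The Synopsis makes this section the operative rule: "no additional subjects will be enrolled in a group if futility criteria are met, as defined in Section 13.6.2".

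Protocol 13.2.2 states that "this design will have a type I error rate (α) of 0.15 and 94% power", with early termination of 77% under the null and 5% under the alternative. It also gives the criterion that Table 15 tabulates: "Group enrollment will be stopped early for futility if the predictive probability of success is less than 6" percent.

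Under Protocol 7.8, disease is assessed before the first dose, "then every 8 or 9 weeks thereafter". Appendix 5 adds at least 4 weeks for confirmation of a response.

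Several places point towards assessed subjects without saying so for the looks:

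- 3.4: "Each group will initially enroll 12 subjects with the option of expanding to a maximum of 30 subjects if futility criteria are not met".
- 5.1: "Subjects may also be replaced in Part 2 of the study for the purpose of testing futility".
- 6.2 defines Part 2 completion by one on-treatment disease assessment.
- 13.4.1 and 13.7.1 define the Efficacy Population and response-evaluable subjects by a post-dose assessment.

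The SAP does not settle it. Section 4.1 plans no formal interim analysis and describes no futility look. Section 5.2 refers back to Protocol 13.6.2. Section 9.1 counts a missing best response as a non-response, but is written for response percentages. Section 11 uses the All Treated population.

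**The concern.** A subject enrolled last week counts towards the 12, 16, 22 or 27 but cannot have a scheduled response. In effect that subject is a non-responder at the look. The error runs one way: it closes groups early on immature data, including groups in which the drug works. If the look is made when the nth subject enrols, that subject is always pending, so at least one pending subject is present at any accrual rate.

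At stake are the stated 94% power and 5% early stopping. So is the agreement between Table 15 and the 6% predictive-probability criterion, since the table was built for n subjects with known outcomes.

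**Working it through.** **Inputs.** From Protocol 13.2.2: null rate 0.10, alternative 0.30, prior Beta(0.2, 0.8), success if posterior P(p > 0.10) is at least 0.80, futility if predictive probability is below 0.06, maximum 30. From Table 15: b(n) = 0 for n = 12–15, 1 for 16–21, 2 for 22–26, 3 for 27–29.

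**Final rule.** With x responders in 30, the posterior is Beta(0.2 + x, 0.8 + 30 − x). P(p > 0.10) is 0.689 at x = 4 and 0.851 at x = 5, so success means at least 5 of 30, in line with the last row of Table 15.

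**Boundaries.** With x responders among m assessed, predictive probability is P(Y ≥ 5 − x), where Y is beta-binomial with size 30 − m and parameters 0.2 + x and 0.8 + m − x. Stopping below 0.06 gives Table 15 and Figure 1 at every n from 12 to 30.

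**The plan's own figures.** Let X(j) be the responders among the first j subjects. Stop at n if X(n) ≤ b(n); succeed if never stopped and X(30) ≥ 5. Exact binomial recursion gives:

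| | p = 0.10 | p = 0.30 |
|---|---|---|
| Success | 0.1486 (stated 0.15) | 94.45% (stated 94%) |
| Early stop | 76.7% (stated 77%) | 4.55% (stated 5%) |
| Expected N | 20.05 (stated 20) | 29.43 (stated 29) |

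The stated figures therefore assume that every counted subject has a known outcome.

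**Literal reading.** With k enrolled subjects pending at each look, the rule becomes: stop at n if X(n − k) ≤ b(n). The final analysis of 30 is taken as fully followed.

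| k pending | Power, p = 0.30 | Early stop, p = 0.30 | Alpha, p = 0.10 |
|---|---|---|---|
| 0 | 94.45% | 4.55% | 0.149 |
| 1 | 93.18% | 6.00% | 0.139 |
| 2 | 91.44% | 7.90% | 0.127 |
| 4 | 86.03% | 13.55% | 0.101 |
| 8 (illustrative) | 61.59% | 38.28% | 0.046 |

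The first look shows the mechanism: 0.7^12 = 1.4% of active groups stop if all 12 are assessed, 0.7^8 = 5.8% if only 8 are.

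**If the group waits at 12 only**, as 3.4 may imply, power and early stop at p = 0.30 are 93.5% / 5.7% (k = 1), 92.2% / 7.2% (k = 2), 87.8% / 11.8% (k = 4) and 79.9% / 19.9% (k = 8, illustrative).

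**Linking k to accrual (assumed).** Poisson accrual per group, first scan at 8 weeks, 100,000 simulated trials per setting (standard error at most 0.16 points), p = 0.30:

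| Accrual per month | Mean pending at 12th enrolment | Power / early stop | Same, wait at 12 only |
|---|---|---|---|
| 0.25 | 1.5 | 92.2% / 7.0% | 92.7% / 6.6% |
| 0.5 | 1.9 | 91.3% / 8.1% | 92.0% / 7.4% |
| 1 | 2.8 | 88.2% / 11.3% | 90.2% / 9.3% |
| 2 | 4.7 | 79.2% / 20.4% | 86.3% / 13.3% |

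**Table 15 against its own criterion.** One pending subject lifts the predictive probability above 6% at three of the four interim steps: 1 response at 16, from 5.0% to 6.8%; 2 at 22, from 5.7% to 8.2%; 3 at 27, from 4.4% to 8.3%. At 0 of 12 it stays below 6% until 8 are pending (0 of 5 gives 5.4%, 0 of 4 gives 7.4%).

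**The case against.** The strongest reply is that assessed subjects were plainly meant. Futility is to be judged by RECIST 1.1 (7.8), which an unscanned subject cannot have. Replacement for futility testing and the Efficacy Population point the same way, and the stated figures are right on that reading. The protocol also says that missing data are not imputed (13.4.4, 13.7). The trigger says after enrolment, not at the instant of it, and data are reviewed on an ongoing basis, so at least one pending subject is not inevitable.

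Much of this is fair as to intent, but none of it defines the count. Replacement is optional and the populations are not linked to Table 15. Setting observed responses against an enrolled total needs no imputation: the pending subject simply moves the row. A delayed look would help, but no delay is stated.

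A second reply is that the 6% criterion limits the harm. Applied to the assessed data, it gives power / early stop of 94.1% / 5.0% with one pending, 93.4% / 5.6% with two and 91.1% / 7.6% with four. Stopping at 0 of 12 with up to seven pending also satisfies it. That limits the size for a team that recalculates predictive probability, but the Synopsis names 13.6.2 as the rule, and 13.6.2 gives the table.

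Third, the large figures rest on assumed accrual, and response is a secondary endpoint in a Phase I study whose Part 2 primary objective is safety. That stands. Treating row 30 as fully followed is a choice that favours the plan: reading it literally as well could only lower power.

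**Conclusion.** The concern holds. The rule as written counts enrolled subjects, and followed as written it does not deliver the stated 94% and 5%. The loss is small with one or two pending (power 93.2% or 91.4%, early stopping 6.0% or 7.9%) and material with four (86.0% and about 14%). Which applies depends on accrual, which the documents do not give; k = 8 and two subjects per month only illustrate the direction.

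The main figures assume a fixed k at every look, responses that appear at the first scan, and complete follow-up at 30. With a 9-week first scan, power at an assumed 0.5, 1 and 2 per month is 90.7%, 87.1% and 76.3%. If 25% of responders respond only at the second scan (assumption), power at 1 per month is 86.6% on enrolled counts, against 93.4% on evaluable counts without a pause. This is a cheap improvement to wording; the boundaries themselves are sound.

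**What to change.** In Protocol 13.6.2, Table 15 and Figure 1, replace the enrolled count with response-evaluable subjects as defined in 13.7.1, plus subjects who left before assessment through progression, death or withdrawal, counted as non-responders. Say which of these 5.1 allows to be replaced, whether enrolment pauses at each look, and whether an unconfirmed CR or PR counts at a look. Keep the boundaries and the maximum of 30. Because SAP 11 records that the study stopped early, the RAP should also report, for each look already made, how many counted subjects had been assessed.

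The cost depends on the pause. If enrolment pauses, the stated figures hold, at up to four pauses per group (12, 16, 22 and 27). If it does not, power (94.5–95.0%) and alpha (0.149–0.157) are essentially kept for one to eight pending. Expected N under the null then rises from 20.1 to 20.8–25.7, and early stopping under the null falls from 77% to as low as 53%. At an assumed 0.5, 1 and 2 per month, expected N under the null is 20.8, 21.4 and 22.8, and early stopping 76%, 74% and 69%; those figures in 13.2.2 would need restating.
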